5.1.11 Pregnancy

If a subject becomes pregnant during the trial, they will immediately stop receiving dupilumab. They will not be followed as there are no published reports of adverse events from pregnancy, fetus and dupilumab.

If the subject becomes pregnant, we will enroll them in a pregnancy exposure registry for women who take DUPIXENT during pregnancy. The purpose of this registry is to collect information about the health of subject and her baby. The registry is <https://mothertobaby.org/ongoing-study/dupixent/>.

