4.6 Subject Completion/Withdrawal

Subjects may withdraw from the study at any time without prejudice to their care. They may also be discontinued from the study at the discretion of the Investigator for lack of adherence to study treatment or visit schedules, AEs, or due to lack of response to dupilumab as defined by esophageal biopsy greater than 15 eosinophils/high power field at week 12. The Investigator may also withdraw subjects who violate the study plan, or to protect the subject for reasons of safety or for administrative reasons. It will be documented whether or not each subject completes the clinical study. If the Investigator becomes aware of any serious, related adverse events after the subject completes or withdraws from the study, they will be recorded in the source documents and on the CRF.

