7.3 Definition of an Adverse Event

An adverse event is any untoward medical occurrence in a subject who has received an intervention (drug, biologic, or other intervention). The occurrence does not necessarily have to have a causal relationship with the treatment. An AE can therefore be any unfavorable or unintended sign (including an abnormal laboratory finding, for example), symptom, or disease temporally associated with the use of a medicinal product, whether or not considered related to the medicinal product.

All AEs (including serious AEs) will be noted in the study records and on the case report form with a full description including the nature, date and time of onset, determination of non-serious versus serious, intensity (mild, moderate, severe), duration, causality, and outcome of the event.

The severity of AEs will be graded according to the following scale:

Mild: Does not interfere in a significant manner with the patient's normal functioning level. It may be an annoyance. Prescription drugs are not ordinarily needed for relief of symptoms but may be given because of personality of the patient.

Moderate: Produces some impairment of functioning but is not hazardous to health. It is uncomfortable or an embarrassment. Treatment for symptoms may be needed.

Severe: Produces significant impairment of functioning or incapacitation and is a definite hazard to the patient's health. Treatment for symptom may be given and/or patient hospitalized.

Injection Site Reactions

The severity of injection site reactions will be graded according to the following scale (semi-colon indicates "or" within description of grade):

Mild: Pain that does not interfere with activity; mild discomfort to touch; <5 cm of erythema or induration that does not interfere with activity

Moderate: Pain that requires repeated use of non-narcotic pain reliever >24 hours or interferes with activity; discomfort with movement; 5.1 cm to 10 cm erythema or induration or induration that interferes with activity

Severe: Pain that requires any use of narcotic pain reliever or that prevents daily activity; significant discomfort at rest; >10 cm erythema or induration; prevents daily activity; requires emergency room visit or hospitalization; necrosis or exfoliative dermatitis

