7.5 Definition of a Serious Adverse Event (SAE)

An SAE is any adverse drug experience occurring at any dose that results in any of the following outcomes:

- death,
- a life-threatening event (at risk of death at the time of the event),
- requires inpatient hospitalization or prolongation of existing hospitalization,
- a persistent or significant disability/incapacity, or
- a congenital anomaly/birth defect in the offspring of a subject.

Important medical events that may not result in death, be life-threatening, or require hospitalization may be considered a serious adverse drug event when, based upon appropriate medical judgment, they may jeopardize the subject and may require medical or surgical intervention to prevent one of the outcomes listed in this definition.

A distinction should be drawn between serious and severe AEs. A severe AE is a major event of its type. A severe AE does not necessarily need to be considered serious. For example, nausea which persists for several hours may be considered severe nausea but would not be an SAE. On the other hand, a stroke that results in only a limited degree of disability may be considered a mild stroke but would be an SAE.

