7.6 IRB/IEC Notification of SAEs and Other Unanticipated Problems

The Investigator will promptly notify the IRB of all on-site unanticipated, serious Adverse Events that are related to the research activity. Other unanticipated problems related to the research involving risk to subjects or others will also be reported promptly. Written reports will be filed using the eIRB system and in accordance with the timeline below. External SAEs that are both unexpected and related to the study intervention will be reported promptly after the investigator receives the report.

Type of Unanticipated Problem	Initial Notification (Phone, Email, Fax)	Written Report
Internal (on-site) SAEs Death or Life Threatening	24 hours	Within 2 calendar days
Internal (on-site) SAEs All other SAEs	7 days	Within 7 business days
Unanticipated Problems Related to Research	7 days	Within 7 business days
All other AEs	N/A	Brief Summary of important AEs may be reported at time of continuing review

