7.6.1 Follow-up report

If an SAE has not resolved at the time of the initial report and new information arises that changes the investigator's assessment of the event, a follow-up report including all relevant new or reassessed information (e.g., concomitant medication, medical history) should be submitted to the IRB. The investigator is responsible for ensuring that all SAE are followed until either resolved or stable.

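### Section 5.1.11 directs that a pregnant subject not be followed and states no return of her outcome from the registry, so a birth defect would reach the trial only passively

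*Combined protocol and SAP*

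**What the plan says.** Section 5.1.11 (Pregnancy) does three things when a subject becomes pregnant during the trial.

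- It stops dupilumab immediately.
- It rules out follow-up by the trial: "They will not be followed as there are no published reports of adverse events from pregnancy, fetus and dupilumab".
- It commits the study team to a hand-off: "we will enroll them in a pregnancy exposure registry for women who take DUPIXENT during pregnancy". Of the registry it says: "The purpose of this registry is to collect information about the health of subject and her baby".

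The safety sections bear on the same outcome.

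- Section 7.5 lists among the outcomes that make an event serious "a congenital anomaly/birth defect in the offspring of a subject".
- Section 7.3 on documentation: "All AEs (including serious AEs) will be noted in the study records and on the case report form".
- Section 7.6.1 on follow-up reports: "The investigator is responsible for ensuring that all SAE are followed until either resolved or stable".

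Two clauses could bring in a late event. Section 4.6 provides for recording in the source documents and on the case report form, with this condition: "If the Investigator becomes aware of any serious, related adverse events after the subject completes or withdraws from the study". Section 7.6, on notifying the IRB, says: "External SAEs that are both unexpected and related to the study intervention will be reported promptly after the investigator receives the report".

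**The concern.** The sentence in 5.1.11 is an instruction, not a silence that a general clause could fill. Staff who obey it make no attempt to learn how the pregnancy ended. The reason it gives is weak, since a lack of published reports is a ground for collecting outcomes. The registry named in the next paragraph of the same section exists to collect them.

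What is at stake is complete SAE recording. A birth defect after exposure in this trial could sit in the registry's files while the trial's safety database and its IRB know nothing of it. Section 7.10.1 makes the principal investigator the safety monitor, so what the investigator learns decides what the trial knows. Efficacy results are not at stake.

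**Working it through.** No arithmetic applies. The documents give no sex mix, pregnancy rate or birth-defect rate, so no probability can be computed. The check is to trace how a pregnancy outcome could reach the trial in the visible text.

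**1. Active routes.** None was found. The registry is mentioned only in 5.1.11, which describes data going into it and says nothing of data coming back.

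**2. Scheduled contact.** Section 3.1.3 ends adverse-event monitoring within 14 days after treatment; section 3.3.1 gives one week. Either is shorter than the remainder of most pregnancies. If the early termination visit in 4.6.1 applies to a pregnant subject, which 5.1.11 does not say, it is a single visit and would usually come before delivery. Table 1 schedules a pregnancy test at Visit 1 only.

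**3. Passive routes.** There are two.

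| Section | Depends on | Limited to |
|---|---|---|
| 4.6 | the investigator happening to learn of the event | serious and related events |
| 7.6, external SAEs | a report reaching the investigator | unexpected and related events |

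Neither makes anyone ask for the outcome. Both are limited to related events, whereas section 7.5.1 wants a relationship rating for each SAE, on a scale that includes unrelated. That rating cannot be made for an event nobody at the site has heard of.

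**4. What the other safety clauses require.**

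- 7.5 defines seriousness. It brings a birth defect within the SAE definition but creates no duty to look for one.
- 7.3 governs documentation. It would put the event on the case report form once known, and it sets no period of active ascertainment.
- 7.6.1 applies to an SAE that was unresolved when first reported. It cannot operate on one that was never reported.

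These clauses say what to do with a birth defect that the trial knows about. Section 5.1.11 removes the ordinary means of knowing, and the registry as described does not restore it.

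**5. Likelihood.** The trial enrols 30 subjects aged 6 to 25. Section 3.4.2 requires a negative pregnancy test at entry. Section 3.4.3 excludes pregnancy and requires contraception until at least 12 weeks after the last dose. Section 5.1.11 stops the drug at once. These provisions lower the chance of the event or the exposure. They do not bear on whether an outcome would be captured.

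**The case against.** The strongest reply is that 5.1.11 must be read whole. The study team itself enrols the subject in a specialist registry, so the outcome is handed over on purpose, and a second copy held by the trial is a preference. Part of this stands. A reader might infer that a birth defect would be recorded nowhere; the documents do not support that, because the registry collects the baby's health and 4.6 leaves a late route open. What remains is that the trial has its own SAE definition and its own IRB, and the registry is given no stated link to either.

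A reader might also infer that 5.1.11 flatly contradicts 7.6.1. It does not, because 7.6.1 acts only on SAEs already reported. Nor does 7.5 by itself oblige anyone to ascertain pregnancy outcomes.

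A third tempting inference is that every birth defect would have to be reported promptly to the IRB. The text of 7.6 asks for events that are unanticipated and related to the research or, for external SAEs, unexpected and related to the intervention. A defect judged unrelated might not qualify even if known. The firm loss is therefore in recording and causality assessment; the loss in IRB reporting is conditional.

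The passive route may also work better than it looks. This is a single-site study that recruits from the site's own programme and clinics (3.3.2, 7.11, 7.12.1), so many subjects may stay in its care. That is a reasonable inference, but it still leaves capture to chance.

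Finally, unseen material could supply a return route: the consent form, SOP 408 (named in 7.2), the data management plan (7.8), the package inserts in a separate appendix (1.3.1.3), or the registry's own arrangements. Even then, 5.1.11 would still tell staff not to follow the subject, and that sentence would need correcting.

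**Conclusion.** The point holds as a gap in SAE capture. A stated rule tells staff not to follow a pregnant subject, and the visible protocol has no active route by which the outcome reaches the trial and two passive ones, both limited to related events. A birth defect might therefore go unrecorded by the trial while the registry holds it.

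The practical size is small. The event is unlikely in 30 subjects under the entry and contraception rules, its rate cannot be estimated, and the primary endpoint and its analysis do not change. The change is still worth making, because the outcome is a serious one and the correction costs little. The conclusion rests on the visible protocol alone and on 5.1.11 being followed as written.

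**What to change.** In section 5.1.11, delete the sentence "They will not be followed as there are no published reports of adverse events from pregnancy, fetus and dupilumab". Keep the immediate drug stop and the registry enrolment. Add:

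*With consent, the investigator will obtain the pregnancy outcome from the subject, the registry or the obstetric record and record it on the case report form; an outcome meeting 7.5 will be recorded as an SAE, assessed for relationship under 7.5.1, and reported to the IRB when it meets the criteria in 7.6.*

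The last clause refers to the criteria in 7.6 on purpose, because meeting 7.5 alone does not trigger prompt reporting there.

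The cost is a few contacts up to delivery for any subject who becomes pregnant, possibly months beyond week 52, and a consent line covering pregnancy and infant outcome data if the consent form lacks one. No study procedure is added and the primary analysis is unchanged. It is a cheap improvement.

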5.1.12 Research Laboratory Tests

The differential gene expression profiles of esophageal biopsies of EoE patients show a marked difference compared to healthy controls and is the EoE disease transcriptome³². This disease gene expression signature was further refined to a smaller gene set to be used as an EoE diagnostic panel (EDP)³³. A gene signature representing type 2 inflammation has been curated from the literature, preclinical experiments performed at Regeneron, and dupilumab response signatures from atopic dermatitis and a phase 2 and 3 study of EoE (Regeneron unpublished data).

In a phase 2 study of EoE (R668-EE-1324), dupilumab significantly decreased the disease, EDP, and type 2 transcriptome signatures. Normalized Enrichment Score (NES) reflects the degree to which the activity level of a set of transcripts is overrepresented at the extremes (top or bottom) of the entire ranked list of transcripts within a sample and is normalized by accounting for the number of transcripts in the set^{34, 35}.

The research bloods that will be collected include:

T cell phenotyping for T1/T2/Th17 expression, blood eosinophilia (CBC) and eosinophilic progenitor cells measured by flow cytometry in peripheral blood.

We will collect patient 6 biopsies and 15 ml peripheral blood at the time of study endoscopy. Patient samples will be provided to laboratory and CAG staff using the deidentified study code. Biopsy tissue will be dissociated in media containing RNase inhibitors and single cell RNA expression libraries will be generated following 10x genomics manufacturer protocols. Peripheral blood mononuclear cell samples will be isolated from patient blood samples and single cell RNA expression libraries will be generated following 10x genomics manufacturer protocols. Single cell RNA libraries will be pooled and sequenced to a minimum depth of 20,000 reads per cell using next generation sequencing (Illumina) at CHOP Center for Applied Genomics (CAG).

Patient sequencing data will be stored using deidentified study codes and will not be associated with patient names or any protected health information. Sequencing data will be transferred

from the CAG to study staff for analysis and stored using CHOP IT managed laboratory data drives (i.e.: <SMB://ressmb>). Sequencing data will not be stored on personal devices. Data analysis will be performed on CHOP managed devices and on the CHOP high performance computing cluster.

Research blood will be done at the following visits 1, 4, 8, 12, and 16

Research esophageal biopsies will be collected at visit 4, 8, 12 and 16.

5.2 Safety Evaluation

Subject safety will be monitored by adverse events, vital signs, physical examinations and endoscopy and biopsy.

If a public health emergency is declared that limits or prevents on-site study visits, regular phone call or virtual calls can occur for safety monitoring and discussion of the patient's health until it is safe for the participant to visit the site again.

5.3 STATISTICAL CONSIDERATIONS

5.3.1 Primary Endpoint

The primary efficacy endpoint will be the change in peak eosinophil counts on esophageal biopsies between 1st and 2nd endoscopy after food introduction in the same patient.

5.3.2 Secondary Endpoints

Secondary endpoints will include the following:

- Maintenance of resolution (<15 eosinophils/HPF on peak measurements) of eosinophilia observed on esophageal biopsies
- Maintenance of remission (<6 eosinophils/HPF on peak measurements)
- Change in mean esophageal eosinophil count from baseline to the end of treatment.
- Change in symptoms scores at the end of treatment compared to baseline
- Interval change on a validated endoscopic scoring system, EREFS
- Interval change on esophageal compliance and distensibility measured by EndoFlip
- Interval change in mRNA transcriptome profile (esophageal tissue), Th2 phenotype (peripheral blood), blood eosinophilia
- Change in the Eosinophilic Esophagitis Quality of Life Score from baseline to the end of treatment

5.4 Statistical Methods

5.4.1 Analysis Populations

An Intent to Treat population (ITTP) will be used as the primary analysis population. This will include all patients that were enrolled in the study.

A Per Protocol population (PPP) will be used as a sensitivity analysis population. This will include all patients that did not have a major protocol violation.

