3.1.1 Disease Control

At the initial phase, research subjects will start on dupilumab based on the dosage used in the 2 phase 3 clinical trials. Based on previous data, patients respond within 12 weeks, therefore, a baseline endoscopy showing a clinical and histologic response will be obtained at week 12. If patients show clinical response with dupilumab as defined as esophagus biopsy with less than 6 eosinophils/hpf. If the biopsy does not improve such that eosinophil count is still greater than 15 eosinophils/hpf, the subject will exit the study. If the biopsy is between 6-15 eosinophils/hpf, the subject will be treated for an additional 12 weeks on dupilumab. If the biopsy is still not less than six eosinophils/hpf, the subject will exit the study. If the subjects have biopsy have less than six eosinophils/hpf (FDA definition of remission), the subjects will advance to food introduction phase of the study.

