3.3 Study Duration, Enrollment and Number of Sites

3.3.1 Duration of Subject Study Participation

If subjects complete all phases, the study will last 52 weeks. 51 weeks of treatment and 1 week of follow-up. If the subject does not meet study criteria (response to dupilumab), they will exit the study at week 13.

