4.6.1 Early Termination Study Visit

Subjects who withdraw from the study will have all procedures enumerated for Visit 8 as the early termination visit.

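### Neither analysis population is limited to subjects who ate a trigger food: the primary result will be responder-only under an intent-to-treat label, and the food-phase secondary analyses mix in dupilumab non-response

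*Combined protocol and SAP*

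**What the plan says.** Section 5.4.1 defines two sets. The intent-to-treat population is primary: "This will include all patients that were enrolled in the study". The per-protocol population is for sensitivity: "This will include all patients that did not have a major protocol violation". A major violation is not defined, and neither set requires that a trigger food was started.

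The design removes some subjects before food. Section 3.1.1 says: "If the biopsy does not improve such that eosinophil count is still greater than 15 eosinophils/hpf, the subject will exit the study". Subjects at 6-15 eos/hpf get 12 more weeks of dupilumab and leave if still not below 6. Section 3.3.1 adds: "If the subject does not meet study criteria (response to dupilumab), they will exit the study at week 13".

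The primary endpoint (5.3.1) is the change in peak count "between 1st and 2nd endoscopy after food introduction in the same patient". Section 5.3.2 lists "Maintenance of remission (<6 eosinophils/HPF on peak measurements") as a secondary endpoint without a denominator. The first study biopsy is at week 12 (Visit 4). Section 3.1.1 calls it the baseline: "a baseline endoscopy showing a clinical and histologic response will be obtained at week 12". Section 5.4.3.4 uses baseline as the GEE reference category.

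Section 4.6.1 says: "Subjects who withdraw from the study will have all procedures enumerated for Visit 8 as the early termination visit". Visit 8 includes an endoscopy with biopsy. No rule for missing data is given. Section 5.6 expects 19 evaluable subjects, and 5.5 treats everything except the primary test as exploratory.

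**The concern.** The trial asks what happens when a known trigger food is eaten on dupilumab. A subject who leaves at week 13 without eating one carries no information on that question, yet belongs to both analysis sets. Three consequences follow.

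- **Primary test.** The reported population would be all enrolled, while the result describes only those who responded to dupilumab and were fed. A subject never fed could also acquire a second endoscopy, and no rule keeps that pair out.
- **Maintenance rates.** With no stated denominator, drug non-response can be reported as failure of food introduction.
- **Biopsy-based GEE and by-time-point means.** Exits with high week-12 counts enter the reference time point and then disappear. The reference mean rises, and a worsening after food looks smaller than it is.

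The last two errors point in opposite directions, so a reader cannot correct for them by eye.

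**Working it through.** **The plan's own figures.** Inputs: 30 enrolled; 64% response, 19 evaluable, effect size 0.7, n = 20, alpha 0.05, power 80% (all 5.6 except the enrolment).
- Evaluable: 30 × 0.64 = 19.2, so 19, as stated. The two quoted rates average (67 + 59.5)/2 = 63.25%, which also gives 19.
- Power of a paired t-test (noncentral t, n − 1 degrees of freedom, noncentrality d√n), taken as two-sided because the plan does not say: 0.844 at n = 20 and 0.823 at n = 19. The stated 80% is met by the 19 fed responders. Thirty pairs, as the population label would suggest, would give 0.959.

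**Exits before food, and the ceiling on maintenance of <6.** The ceiling is (number fed)/30. It assumes that exits stay in the denominator, count as not maintained, and that nobody at 6-15 advances later.

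| Response rate (source) | Fed | Exits | Ceiling |
|---|---|---|---|
| 50% (lower bound implied by 7.10.3) | 15 | 15 | 50% |
| 58.8% (7.10.3) | 18 | 12 | 60% |
| 64% (5.6) | 19 | 11 | 63% |
| 67% (5.6, phase 2) | 20 | 10 | 67% |
| 22/26 (1.3.1.1, site data) | 25 | 5 | 83% |

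Each 6-15 subject who later advances adds 1/30 = 3.3 points. If all 19 fed subjects stay below 6, the two denominators give 19/30 = 63% (exact 95% CI 44-80%) or 19/19 = 100% (82-100%). If 15 of the 19 do (assumed), they give 15/30 = 50% (31-69%) or 15/19 = 79% (54-94%).

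**GEE and raw means.** Take two time points, an identity link, equal variances and working correlation ρ. Let m exits have a mean week-12 count that is g above the fed subjects' mean, and no later value. The estimated change is then: true change − (1 − ρ)(m/30)g. Correlation 0 is the plain difference in raw means. The true change is set at +11, the detectable difference in 5.6, for illustration; m = 11.

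| Gap g | ρ = 0 | ρ = 0.5 |
|---|---|---|
| 1 | 11 − 0.37 = +10.6 | 11 − 0.18 = +10.8 |
| 8.9 | 11 − 3.28 = +7.7 | 11 − 1.64 = +9.4 |

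A gap of 1 is the case where fed subjects sit at 5 and exits at 6. The 8.9 borrows phase 3 data and assumes that 59.5% below 6 (5.6) and 64% below 15 (1.3.1.1) both describe the 42 Part A subjects on dupilumab (7.10.2.4). That means 25 and 27 subjects, leaving 15 at 15 or more and 2 at 6-14. With fed subjects at 5 or less, the gap is at least (15 × 10 + 2 × 1)/17 = 8.9.

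**What is not affected by exits that have no later value.** Within-subject changes (5.4.3.2) and paired tests (5.4.3.3) use complete pairs. Symptom and quality-of-life scores have their baseline at Visit 1, and no claim is made about them.

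**Unfed second biopsy.** There are two routes: the early-termination procedures in 4.6.1, if an exit counts as a withdrawal, and the repeat biopsy that 3.1.1 implies for subjects at 6-15. The documents do not say how many such pairs to expect or what change they would show, so this has no computable size.

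**The case against.** The strongest reply is that little is at risk. The endpoint definition already confines the primary test to subjects with a biopsy after food, 5.6 openly plans for 19, and the rest is exploratory in an open-label pilot. Subject-level listings are promised (5.4.3.2), so any denominator could be rebuilt. This stands as a limit on severity. It does not supply a prespecified denominator, and choosing one after seeing the data is the risk.

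A reader might infer that the plan itself caps maintenance at 63%. It does not. The cap requires exits to be both kept and scored as not maintained, and no section says so. One can argue that a subject who never reached remission cannot maintain it and drops out naturally. That is a fair reading, but the all-enrolled label is then wrong for this endpoint too.

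A reader might also take 8.9 as the smallest gap the documents allow. It is not. It pools another trial's rates, which may not refer to the same subjects or week, and this trial's rules allow a gap near 1, where the effect is trivial. Section 5.4.3.4 also leaves the distribution and covariance to be chosen from the data.

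Nor is it certain that exits have no later biopsy, given 4.6.1 and the extra 12 weeks for subjects at 6-15.

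Finally, the first primary aim (2.1) concerns dupilumab's efficacy in allowing food introduction. On that reading, never reaching food is a failure of the overall strategy. This is a legitimate second question, and it deserves its own labelled result.

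**Conclusion.** The point holds in limited form. Both populations retain subjects who leave as directed before any food: about 11 of 30 at the plan's rate, 5 to 15 over the documents' rates.

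For the primary test the fault is mainly the label. A reader might infer that non-responders bias or weaken the test, but a complete-pair analysis leaves them out, and 19 pairs give 82% power. This rests on complete pairs being used, since no imputation rule is stated. The remaining gap is that an unfed second biopsy is not excluded.

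For maintenance of <6, the ceiling of about 63% is conditional on how exits are counted and on the 64%. For the GEE and raw means, the direction is clear where exits have high week-12 counts and no later value: a rise after food is understated. The size runs from negligible to about 3 eos/hpf in the illustrations and cannot be fixed from the documents.

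This should be corrected before analysis, but it does not threaten the trial.

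**What to change.** Define a food-introduction efficacy set: every subject who takes at least one serving of a trigger food, whatever the later adherence or diet change. Baseline is the last biopsy before food, and only biopsies after food has started count as follow-up.

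- Use this set for the primary test and for the food-phase by-time-point and GEE comparisons, and nest the per-protocol set in it.
- For maintenance of <6 or <15, use as denominator the members of the set who were below that threshold at the pre-food biopsy.
- Report how many fed subjects lack a post-food biopsy, and show the primary result with and without early-termination biopsies.
- Keep all enrolled for safety and for the week-12 response rate. Optionally report the all-enrolled proportion as a clearly labelled overall-strategy result.

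The conditions for starting food differ between the synopsis (no active biopsy, defined as above 15, plus decreased symptoms) and 3.1.1 (below 6). They must be reconciled, because they determine who is in the set.

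The cost is SAP wording plus a protocol clarification of those two passages; no new data are needed. The downside is that conclusions become conditional on response to dupilumab, which 5.6 already assumes.
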